7.2.1 Stopping Rules

The following stopping criteria will be implemented:

1. Subject stopping criteria: If a subject experiences an AE that is deemed by the clinical center Principal Investigator to be at least “possibly” drug-related and is Grade ≥ 2 in severity (using the Common Terminology Criteria for Adverse Events (CTCAE v 5), that subject will be withdrawn from dosing, return for all scheduled evaluation visits, and be followed until the AE resolves or stabilizes.

2. Cohort stopping criteria: If 1 subject in a cohort experiences an AE that is deemed by the clinical center Principal Investigator to be probably or definitely drug-related and is Grade ≥ 3 in severity by CTCAE, or if 2 subjects in a cohort experience AEs that are deemed by the clinical center Principal Investigator(s) to be at least “possibly” drug-related and are Grade $>/= 3$ in severity by CTCAE, dosing further subjects will be suspended until data is reviewed by the sponsor.
3. Dose stopping criteria: If the Acne Vulgaris is deemed as cleared by the study investigator (IGA=0), the subject will be instructed to stop dosing or continue based on the discretion of the clinical center investigator. Acne Vulgaris should be considered clear if it is not showing any inflammatory signs of disease. If it is decided by the local investigator to stop drug treatment, the clinical center investigator will determine which of the following scenarios will be implemented :
 - The subject should return to the clinical center weekly for further assessment.
 - The subject should return the following week to complete the end of study (Day 43) follow up visit.

If the subject is still in the study, and the Acne Vulgaris returns, the subject should contact the clinical center and resume treatment (through Day 28) and weekly visits until the planned Day 43.

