9.4 Randomization Schedule

The sponsor or designee will generate the randomization schedules. Randomization will occur once final eligibility is confirmed after completion of the screening procedures.

Part A of the study is not blinded. All subjects will receive BMX-010.

Part B of the study is double-blind, where both the subject and the clinical center staff will be blinded to the treatment assigned. BMX-010 and Placebo will be dispensed 2:1 (study drug: placebo).

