13.1.1 Reporting of AEs

BioMimetix JV, LLC, should be notified of all treatment-related AEs on a regular basis (to be agreed upon by the study team and BioMimetix JV, LLC). Reports of these should be made to [name], PhD, at [contact] (cell).

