13.2.1 Reporting of SAEs

Only AEs that the sponsor and/or Principal Investigator determines to be serious, unanticipated, and related or possibly/probably (i.e., more likely than not) related to the research must be reported to the IRB. Those AEs will be submitted, according the following guidelines:

- Report within 24 hours of learning about any subject's death that was unanticipated and more likely related to the research than unrelated;
- Report within 5 business days of learning about any serious, unanticipated, and related or possibly/probably related AE;
- Report within 10 business day of learning about any other unanticipated problem or event that was more likely related to the research than unrelated.

The Principal Investigator is responsible for compliance with all applicable regulations pertaining to the reporting of AEs to the IRB. To ensure patient safety, each study treatment-related serious adverse event (SAE) will also be reported to the sponsor, BioMimetix JV, LLC, within 24 hours by the Principal Investigator. Follow-up information on these events shall also be reported to BioMimetix JV, LLC, within 24 hours of receipt. Follow-up information may include hospital admission records, discharge summaries and autopsy reports, where applicable. The sponsor must report to the Food and Drug Administration (FDA), in an Investigational New Drug (IND) safety report, any suspected adverse reaction that is both serious and unexpected. Before submitting this report, the sponsor needs to ensure that the event meets all three of the definitions contained in the requirement:

- Suspected adverse reaction (i.e., there is a reasonable possibility that the drug caused the AE)
- Serious
- Unexpected

If the AE does not meet all three of the definitions, it should not be submitted as an expedited IND safety report.

The sponsor is required to report to the FDA all IND Safety reports in writing within 15 days (7 days for unexpected fatal or life-threatening suspected adverse reaction). The FDA Form 3500A can be found on the FDA website, www.fda.gov. All other AEs will be reported to the FDA in the IND Annual Report.

In addition to the above mentioned reporting responsibilities, after discontinuation of the study, all SAEs considered to be drug related will be reported to BioMimetix JV, LLC, by the Principal Investigator.

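### A non-serious Grade 3 or higher related AE can trip the cohort stopping rule, but the protocol sets no time for it to reach the sponsor and names nobody to count across sites

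*Protocol*

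**What the plan says.** Protocol 7.2.1 sets a cohort stopping rule with two limbs, both for AEs of CTCAE Grade 3 or higher.

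- One-subject limb: "If 1 subject in a cohort experiences an AE that is deemed by the clinical center Principal Investigator to be probably or definitely drug-related".
- Two-subject limb: "if 2 subjects in a cohort experience AEs that are deemed by the clinical center Principal Investigator(s) to be at least" possibly related.

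The consequence of either is that "dosing further subjects will be suspended until data is reviewed by the sponsor". The two-subject limb allows for more than one investigator, and the synopsis allows up to 20 centers.

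Reporting to the sponsor is set elsewhere, by a different criterion. Under 13.1.1 the sponsor "should be notified of all treatment-related AEs on a regular basis (to be agreed upon by the study team" and the sponsor. Under 13.2.1, "each study treatment-related serious adverse event (SAE) will also be reported to the sponsor", within 24 hours. Section 13.2 defines serious by a list of outcomes, and CTCAE grade is not on that list.

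The term cohort is not defined in 7.2.1. Its only other use is the title of 9.1.1, which lists a QD row and a BID row for Part A and a single entry for Part B.

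**The concern.** The rule is keyed to grade and attribution, while the fast reporting route is keyed to seriousness. An event can therefore meet the stopping rule and still travel by the slow route. For a topical product this case is easy to picture: section 10.2 lists skin irritation at the application site and light-activated rash among the possible effects, and a severe reaction of either kind need not be serious.

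This is the only pre-specified stop at group level; 14.5 plans no interim analysis. It asks the sponsor to review before more subjects are dosed, and its second limb needs someone to add up events from different centers. The protocol assigns that task to nobody. If the sponsor hears late, centers that have seen no event have no reason to pause. A treatment course lasts at most 28 days, so if the agreed interval were about a month (none is stated), a subject starting elsewhere after the trigger could finish the course before the sponsor learned of it.

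**Working it through.** The protocol states no operating figure for this rule, so there is none to reproduce. The check is mainly a comparison of sections.

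**Step 1. Route taken by each kind of Grade 3 or higher event**

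| Event | Effect under 7.2.1 | Time to reach the sponsor |
|---|---|---|
| Treatment-related and serious | Triggers, or counts toward, the rule | 24 hours (13.2.1) |
| Probably or definitely related, not serious | Triggers the rule alone | Interval to be agreed (13.1.1) |
| Possibly related, not serious | Counts as one of two | Interval to be agreed (13.1.1) |

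The last two rows are the gap: 7.2.1 gives these events an effect on dosing, and section 13 gives them no stated time to reach the sponsor.

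**Step 2. What a site can do unaided**

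- One-subject limb: the investigator who judges the event knows that it qualifies, so that site can suspend at once. The other centers, up to 19, cannot know until someone tells them.
- Two-subject limb, both events at one site: that site can again see the trigger.
- Two-subject limb, events at two sites: each investigator sees one event, which is below the limit. Only a party holding reports from both can see the trigger.

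**Step 3. How often a two-subject trigger would span sites**

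Inputs from the documents: up to 150 subjects in Part B (9.1.1) and up to 20 centers (synopsis). Assumptions: Part B is one cohort, subjects are spread evenly over sites, and every subject is equally likely to have an event. With m subjects per site, the chance that the second affected subject is at the first one's site is (m − 1)/(150 − 1).

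- 20 sites: m = 150/20 = 7.5, so 6.5/149 = 4.4% at the same site and 95.6% across sites.
- 5 sites (an assumed lower number): m = 150/5 = 30, so 29/149 = 19.5% at the same site and 80.5% across sites.

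Uneven site sizes or clustering of events within sites would raise the same-site share. Unless enrolment is concentrated in very few centers, most two-subject triggers would be invisible to any single investigator.

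**Step 4. Whether other provisions close the gap**

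- Section 13.1 requires every AE to be recorded in the CRF, and 15.3.1 gives the sponsor access to the electronic database. Neither sets a deadline for entry, and 15.3.2 allows paper.
- Section 13.2 includes medically significant conditions among serious outcomes, so an investigator may judge some Grade 3 events serious. This rests on individual opinion and is not linked to the cohort rule.

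Both soften the gap, but neither gives a qualifying event a stated time to reach the sponsor.

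**The case against.** The strongest reply is that the protocol already protects subjects in practice. The affected subject stops dosing locally for any at least possibly related AE of Grade 2 or higher. The investigator who judges a single-subject trigger can apply it on the spot, and a required sponsor review implies a call to the sponsor. Section 13.1.1 gives a direct telephone contact, the sponsor can see the database, and some Grade 3 reactions would be reported as serious anyway.

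Most of this stands for the reporting site and the affected subject. It does not reach the other centers, or two events at two centers, because none of these provisions sets a time or names anyone to add up the count.

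A reader might also infer more than the documents support:

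- That any single related Grade 3 event stops dosing. One subject suffices only when the relation is probable or definite; at the level of possible, two are needed.
- That the count cannot be made in Part B because "both the subject and the clinical center staff will be blinded to the treatment assigned". This limits site staff only. Section 9.1.1 gives Part B as one entry, and a count over Part B as a whole needs no unblinding. A count by arm could be made by the sponsor personnel with unblinded access in 9.1.2.
- That the unclear meaning of cohort changes the chance of a stop dramatically. Setting a small Part A treatment cell against all of Part B compares different groups of subjects, not two readings of one cohort, and the protocol gives no event rate.

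**Conclusion.** The point holds as a mismatch between two stated rules. Section 7.2.1 acts on grade and attribution across centers, whereas section 13 sends events promptly to the sponsor only if they are serious. Followed as written, the rule can stop the site that sees a single trigger, but it cannot promptly stop the others or reliably detect a trigger split between sites.

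On size, about 81% to 96% of two-subject triggers in Part B would span sites for 5 to 20 equally sized centers, under the assumptions in the working. This describes where pairs fall, not how often they occur. The number of extra subjects dosed before the sponsor hears cannot be given, because the protocol states neither an enrolment rate nor a notification interval.

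The undefined cohort is a matter for clarification and is secondary to the reporting gap. This should be corrected, and it belongs in the protocol, since stopping rules and AE reporting are set there and not in a SAP. The grade and number thresholds are not at issue.

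**What to change.** 1. Reconcile 7.2.1, 13.1.1 and 13.2.1 so that every AE able to trigger or count toward the cohort rule, serious or not, reaches the sponsor by the expedited route already in 13.2.1. Wording this by grade and attribution category, as 7.2.1 does, makes plain that possibly related events are included.
2. Name the sponsor role that keeps the count across sites, declares a trigger and notifies all centers.
3. As a clarification, tie cohort in 7.2.1 to the list in 9.1.1. If Part B is one cohort, say so. If the count is by arm, assign it to the unblinded personnel in 9.1.2.

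The cost is a few sentences of protocol text and a few more expedited reports from sites.

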Part B is a randomized, double-blind, multi-center, placebo-controlled study of adult men and women with Acne Vulgaris. Subjects will be randomized and dosed with BMX-010 0.03% or 0.1% with the frequency of dosing (either QD or BID) for each dose of the study drug as determined optimal in Part A of this trial. Dosing will occur for a minimum of 7 days and a maximum of 28 days. An overview of the study design is presented in the schematics below, and details of study activities are provided in **Table 4a**.

In the Part A study, up to a total of up to 60 evaluable subjects with Acne Vulgaris will be dosed with BMX-010 (0.03% or 0.1%) topically applied either QD or BID. All subjects will dose for a minimum of 7 days and a maximum of 28 days. The dosing strength, formulation, frequency, and time frame will be at the discretion of the local clinician.

The sponsor may close enrollment once enough data has been obtained to determine the optimal dosing frequency and duration of dosing for each concentration (0.03% or 0.1%) of BMX-010 cream or gel to be studied in Part B.

In the Part B study, up to 150 evaluable subjects with Acne Vulgaris will be dosed with the concentration and formulation of BMX-010 determined optimal in Part A or Placebo given at the frequency determined optimal in Part A. The randomization scheme is 2:1, study drug : Placebo. All subjects will dose for a minimum of 7 days and a maximum of 28 days.

The sponsor may close enrollment once enough data has been obtained to assess the expected efficacy of 0.03% BMX-010 and 0.1% BMX-010. This data will be used to plan future studies.

The Investigator Global Assessment (IGA) is a five scale (0 to 4) static evaluation of overall Acne Vulgaris severity (as described below).

Investigator Global Assessment (IGA) Scale

Grade	Description
0 = Clear	Clear skin with no inflammatory or noninflammatory lesion
1 = Minimal	Almost clear, rare noninflammatory lesions with no more than one small inflammatory lesion
2 = Mild	Mild, some noninflammatory lesions, no more than a few inflammatory lesions
3 = Moderate	Moderate, up to many noninflammatory lesions and may have some inflammatory lesions, but no more than one small nodular lesion
4 = Severe	Severe, up to many noninflammatory and inflammatory lesions, but no more than a few nodular lesions

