5 BACKGROUND

Acne is a very common chronic inflammatory disease. Acne ranging from moderate to severe affects around 20% of young people. Acne continues to persist into the 20s for 64% of individuals and 30s for 43% of individuals [1].

There are systemic and topical treatments currently on the market for the treatment of acne. These products can cause severe side effects, thus new and innovative therapies are needed. Additionally, acne is known to cause significant psychological morbidity in patients [2].

Acne lesions are either noninflammatory (open and closed comedones, called whiteheads and blackheads) or inflammatory (papules and pustules) [2].

BioMimetix JV, LLC, has developed a topical gel and a topical cream formulation of BMX-010 for the treatment of inflammatory skin diseases, such as Acne. BMX-010 (MnTE-2-PyP) is a manganese (Mn) porphyrin drug; porphyrins are made up of 4 pyrrole rings connected by methine bridges. These molecules often form complexes with metals by incorporating them into the nucleus of the porphyrin structure, situated between the interiorly-located vertices of the pyrrole rings. Such Mn-porphyrin-based compounds are potent anti-inflammatory agents that can catalytically inactivate a range of reactive oxygen species, including peroxynitrite and superoxide anion [3,4].

BMX-010 (MnTE-2-PyP) exhibits extremely high enzymatic redox activity for a broad range of oxidant species including O₂-, H₂O₂, and ONOO- (ROS). The drug has catalytic antioxidant activity capable of scavenging ROS as well as the mimicking of superoxide dismutase. Unlike other antioxidants, this class of agents is catalytic and can repetitively eliminate ROS. BMX-010 acts as a scavenger in the cell cytoplasm, as in the context of reduced TACE oxidation [5] and yet functions as an oxidizer in the nucleus, inhibiting the reduction of the p50 subunit of NF-κB and effectively blocking DNA binding [6]. As a result of the complex mechanism of action, BMX-010 and other metalloporphyrin compounds exhibit an unexpected potency in inflammatory injury models at doses 100 to 1000 times less than would be expected if they were acting primarily as stoichiometric antioxidants [7,8]. BMX-010 and related compounds mechanism of action is reflected in diverse preclinical models.

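### Section 7.2.1 calls acne clear once inflammatory signs are gone, so sites may stop dosing in subjects who are not IGA 0

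*Protocol*

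**What the plan says.** Criterion 3 of Protocol Section 7.2.1 opens with a numeric trigger: "If the Acne Vulgaris is deemed as cleared by the study investigator (IGA=0"). The investigator then chooses between stopping and continuing. The next sentence gives a second test: "Acne Vulgaris should be considered clear if it is not showing any inflammatory signs of disease".

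If dosing stops, the subject either keeps coming weekly or takes this route: "The subject should return the following week to complete the end of study (Day 43) follow up visit". There is one way back onto treatment, which ends at Day 28: "If the subject is still in the study, and the Acne Vulgaris returns, the subject should contact the clinical center and resume treatment".

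Sections 7.1 and 7.2 also allow stopping on full clearing as judged by the investigator, with the last evaluation at Day 29 or Day 43. They recommend 28 days of treatment to everyone and do not define full clearing.

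Section 5 separates the lesion types: "Acne lesions are either noninflammatory (open and closed comedones, called whiteheads and blackheads) or inflammatory (papules and pustules"). Grade 0 on the Synopsis IGA reads "Clear skin with no inflammatory or noninflammatory lesion". Section 11.1 prints a different five-grade scale based on papules, pustules and erythema, and its grade 0 does not mention comedones.

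**The concern.** The two tests for clear sit side by side in one dosing rule and can give different answers for the same face. A subject whose papules and pustules have gone but whose comedones remain passes the second test and fails the first, if the Synopsis acne scale is used. That is the only printed scale that grades comedones, and the trial counts noninflammatory lesions for a secondary objective in both parts.

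At a true IGA 0 the subject has already met the responder definitions at that visit, and the resume clause covers acne that comes back. A subject stopped with comedones has often not met them. The resume clause does not help either, because the comedones have persisted rather than returned. Visit-by-visit IGA scores and lesion counts would show afterwards who was affected, but no analysis can restore dosing that was withheld.

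**Working it through.** There is no plan figure to reproduce. The check compares the texts and then counts grade combinations.

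**Step 1. Grade a comedone-only face (no inflammatory lesion) on the Synopsis IGA.**

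| Grade | What the scale requires | Fits a comedone-only face? |
|---|---|---|
| 0 | "Clear skin with no inflammatory or noninflammatory lesion" | No |
| 1 | Rare noninflammatory lesions, at most one small inflammatory lesion | Yes, if comedones are rare |
| 2 | "Mild, some noninflammatory lesions, no more than a few inflammatory lesions" | Yes; a few is a ceiling, so zero qualifies |
| 3 | "up to many noninflammatory lesions and may have some inflammatory lesions", with at most one small nodule | Yes; inflammatory lesions are optional |
| 4 | Noninflammatory and inflammatory lesions together | No |

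Such a face is grade 1, 2 or 3. It meets the second sentence of criterion 3 and fails the IGA 0 trigger.

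**Step 2. Check eligibility.** Section 8.1 requires IGA of 2 or more at screening and baseline and sets no minimum inflammatory lesion count. Read literally, an eligible comedone-only subject at grade 2 or 3 meets the sentence before any treatment.

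**Step 3. Check responder status at the visit where the subject is called clear.** Inputs are baseline grade 2, 3 or 4 (Section 8.1), and Part B primary objectives 2 and 3 (Section 6.1). A 2-grade improvement is read as at least 2. The current comedone-only grade is 1 to 3 and no worse than baseline.

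- Pairs (baseline, current): (2,1), (2,2), (3,1), (3,2), (3,3), (4,1), (4,2), (4,3). Total 8.
- Miss objective 2 (baseline − current < 2): (2,1), (2,2), (3,2), (3,3), (4,3). That is 5 of 8.
- Miss objective 3 (baseline − current < 2, or current > 1): those five plus (4,2). That is 6 of 8.
- At IGA 0: (2,0), (3,0), (4,0) improve by 2, 3 and 4 grades. None of 3 misses either objective at that visit.
- Leaving out the two pairs with no improvement, (2,2) and (3,3), 3 of 6 miss objective 2 and 4 of 6 miss objective 3.

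**Step 4. Bound the loss for one affected subject** (nominal days, ignoring the ±2-day windows). This loss comes from the option to stop, so it would be the same for a stop at IGA 0.

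| Stopped at | Dosing days given | Dosing days lost | Final visit by the following-week route | Days before Day 43 | Of 5 post-baseline visits, not held |
|---|---|---|---|---|---|
| Day 8 | 7/28 = 25% | 21 | Day 15 | 43 − 15 = 28 | 3 |
| Day 15 | 14/28 = 50% | 14 | Day 22 | 43 − 22 = 21 | 2 |
| Day 22 | 21/28 = 75% | 7 | Day 29 | 43 − 29 = 14 | 1 |

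Under Sections 7.1 and 7.2 the final evaluation is instead Day 29 (14 days early, 1 of 5 visits not held) or Day 43 (none lost). The following-week route conflicts with those sections, which is a separate problem.

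**The case against.** The case for leaving the sentence alone, or treating it as a minor clarification, has several parts.

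- **The trigger is numeric.** The site must read the second sentence as overriding the IGA 0 beside it, having just scored that face 1, 2 or 3. Many investigators would not. This limits how often it happens, but the sentence is a direct instruction on how to judge clear, and Sections 7.1 and 7.2 offer no definition to set against it.
- **Stopping is discretionary and 28 days is recommended.** True. But that discretion starts once the subject is deemed clear, and the faulty sentence governs that step.
- **The conflict depends on the scale.** On the Section 11.1 scale, a comedone-only face without erythema could be grade 0, and the two tests largely agree. This stands, and the two printed scales are a defect in themselves. Settling on the Synopsis scale alone would still leave the sentence wrong.
- **The counts are not proportions.** Grade pairs are weighted equally, and the no-improvement pairs are the least likely to be called clear. This stands; without them the counts fall to 3 of 6 and 4 of 6.
- **The contrast with IGA 0 is too clean.** Objective 3 uses the final IGA, so a subject stopped at a true 0 can relapse and miss. This stands, and the 0 of 3 holds only at the stopping visit.
- **The lost dosing days and visits are not specific to this sentence.** This stands. They show what a wrong stop can cost one subject and add nothing about frequency.
- **The trial is exploratory, and the label does not itself alter a recorded IGA.** Also true, but the dosing behind later scores can change.

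**Conclusion.** The concern holds. Criterion 3 contains two tests for clear that disagree on the Synopsis acne IGA, and a site following the second may stop product in a subject at grade 1, 2 or 3. In 5 of 8 possible grade pairs that subject does not yet meet Part B objective 2, and in 6 of 8 does not meet objective 3, against 0 of 3 for both at a true IGA 0 at that visit. The most one subject can lose is 21 of 28 dosing days.

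This rests on the Synopsis scale being the one in use and on reading a 2-grade improvement as at least 2. The textual conflict is certain; the number of subjects affected and the effect on any endpoint cannot be estimated from the protocol. It should be fixed because it is a stated dosing rule that misdirects if followed, and the correction is small.

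**What to change.** Delete the second sentence of criterion 3 in Section 7.2.1, or replace it with: *Clear means IGA = 0 on the Synopsis acne scale (no inflammatory or noninflammatory lesions).* Print that same scale in Section 11.1. Investigator discretion to stop or continue at IGA 0 can stay, and the event definition for time to full clearing can be left to the SAP.

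The cost is one sentence, one table and a clarification to sites, with no new assessments. The downside is that fewer subjects will be labelled cleared and allowed to stop early. The change does not remove the early-stop options, nor does it resolve the conflict between the following-week final visit and the Day 29 or Day 43 evaluation, which needs its own correction.
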